7.5.5 Unblinding Regulations

Unblinding of this clinical trial will be conducted after obtaining the serum test results of all participants at 28 days after the second dose, which will be jointly implemented by the sponsor, principal investigator, and statistical party. After unblinding, personnel responsible for subject observation, result judgment, and data verification will remain blinded until the final database is locked.

7.6 Clinical Trial Flowchart

The flowchart of this clinical trial is shown in Figure 1.

[figure not shown]

Figure 1 Flowchart of Phase III Clinical Trial

7.7 Study duration

7.7.1 Duration of the Study

Table 9 Study period

Items	Period
Trial preparation (site selection, protocol and case report form design; ethical review; site registration; application to the Ethics Committee for Genetic Resources; database set-up; subject recruitment, etc.)	3 months
On site operation +Data collection +Antibody detection	10 months
Statistical analysis	1 month
Finish clinical study report	1 month
Total	15 months

7.7.2 Duration of Subject Participants

The expected period is no less than 7 months for each participant.

7.8 Suspension and early termination

The Criteria of the trial suspension:

- (1) Occurrence of one or more the Grade 4 vaccine-related adverse events (local and systemic), or fatal or life-threatening SUSARs;
- (2) Occurrence of Grade 3 or above adverse events in $\geq 15\%$ participants or more, including local reactions, systemic reactions and vital signs.

The Criteria of early termination of the trials:

- (1) The sponsor requests termination of the trial and provides the reasons;
- (2) EC requests termination of the trial and provides the reasons;
- (3) The requests termination of the trial and provides the reasons; and
- (4) After the clinical trial is suspended, the investigator and the sponsor shall discuss whether to terminate the trial or not.

When the occurrence of adverse events meets the suspension criteria, the trial will be suspended first through determination of investigators and the sponsor. In case of disagreements between investigator and the sponsor, the investigators' judgment shall prevail. Secondly, the suspension shall be reported to the national drug regulatory department and EC, as well as be informed to the participants. On the basis of analyzing the relevance of the adverse events as well as the severity and safety risks, an investigation report will be formed. Relevant parties to jointly decide whether to continue the clinical trial.

7.9 Protocol deviation

Protocol deviation refers to any non-compliance with the clinical trial protocol design or procedures. Protocol deviation includes the behaviors that have no effect on the rights and interests, safety and benefits of the participants, or the completeness, accuracy and reliability of the trial data, as well as the evaluation on the safety or key indicators of the protocol; and major protocol deviation (protocol

violation) includes affecting the rights, interests, safety and benefits of participants, or the integrity, accuracy and reliability of test data, as well as the evaluation of endpoints.

Participants with major protocol deviations should be given special attention, and safety information should be collected to ensure their safety. For any protocol deviation occurring during the study, investigators shall record it in detail, report it to the principal investigator and the sponsor, and submit it to the EC as required. The principal investigator and the sponsor shall determine whether participants with protocol deviations will continue to complete the subsequent study procedures.

The list of major protocol deviations includes (but is not limited to):

- (1) Failure to obtain informed consent from the participants' guardians;
- (2) Enrollment of participants who do not meet the inclusion criteria or meet the exclusion criteria;
- (3) Incorrect vaccination of participants with the trial vaccine;
- (4) Report serious adverse events (SAEs) without the specified time;
- (5) Vaccination with any influenza vaccine other than the trial vaccine during the study period;
- (6) Vaccination of the trial vaccine outside the window period;
- (7) Blood collection outside the window period;
- (8) The interval between vaccinations does not meet the requirements (including emergency vaccination in response to urgent events).

8. Participants

8.1 Inclusion criteria

- (1) Children in stable health aged 6-35 months;
- (2) Children's guardians are able to provide legal identity documents and immunization certificates;
- (3) Obtain the written informed consent of the participant's guardian;

8.2 Exclusion criteria for the first dose of vaccination

- (1) History of the seasonal influenza vaccine for the 2023-2024 influenza season, or have a vaccination schedule during the trial;
- (2) History of seasonal influenza in the past 6 months;
- (3) Axillary temperature $>37.0^{\circ}\text{C}$ before vaccination;
- (4) History of allergy to the vaccine or vaccine ingredients, and have serious adverse reactions to the vaccine, such as urticaria, dyspnea, and angioneurotic edema;
- (5) Congenital malformations or developmental defects, genetic defects, severe malnutrition, or asthma;
- (6) Serious chronic diseases (Down's syndrome, diabetes, or sickle cell anemia);
- (7) Severe nervous system disorder (epilepsy, seizure or convulsion) or psychotic disorder;
- (8) Autoimmune diseases (e.g., systemic lupus erythematosus) or immunodeficiency/immunosuppression (e.g., AIDS, post organ transplant);
- (9) History of thyroidectomy, asplenia, functional asplenia, and asplenia or splenectomy under any circumstance;
- (10) Coagulation abnormalities (such as coagulation factor deficiency, coagulation disease and platelet disorder), obvious bruise or coagulation defects from a doctor's diagnosis;
- (11) Has received continuous treatment with corticosteroids or other immunosuppressants (excluding corticosteroid spray therapy for allergic rhinitis and surface corticosteroid therapy for

acute uncomplicated dermatitis) and cytotoxic therapy for ≥ 14 days in the past 6 months;

- (12) Acute diseases in recent 3 days;
- (13) Has received blood products in past 3 months;
- (14) Has received other investigational drugs within 30 days;
- (15) Has received live attenuated vaccines within 14 days or subunit or inactivated vaccine within 7 days;
- (16) Has participated in other clinical trials before enrollment and is within the follow-up period, or plan to participate in other clinical trials during the clinical trials;
- (17) Any other factors that are inappropriate for participation in the clinical trial by investigator's judgment.

8.3 Exclusion criteria for the second dose of vaccination

If one of the following (1) to (4) conditions occur, the participant is not allowed to continue vaccination at the discretion of the investigator. If one of the following (5) to (6) conditions occur, the investigator shall determine whether the participant continues vaccination. If one of the following (7) to (10) conditions occur, the participant may receive postponed vaccination within the time window specified in the protocol.

- (1) Influenza vaccine other than the investigational vaccine is used during the study;
- (2) Any SAEs related to vaccination of participants occur;
- (3) Severe allergic reaction or hypersensitivity reaction occurs after vaccination (including urticaria/rash within 30 min after vaccination);
- (4) Any confirmed or suspected autoimmune or immunodeficiency disease occurs, including human immunodeficiency virus (HIV) infection;
- (5) Acute onset of chronic disease or emerging chronic disease occurring after vaccination;
- (6) Other reactions occur as judged by the investigator, including severe pain, severe swelling, severe limitation of motion, persistent hyperpyrexia, severe headache or other systemic or local reactions;
- (7) An acute disease occurs at the time of vaccination (acute disease is a moderate or severe disease with or without pyrexia);
- (8) Axillary temperature $>37.0^{\circ}\text{C}$;
- (9) The subunit vaccine or inactivated vaccine is inoculated within 7 days, or the live attenuated vaccine is inoculated within 14 days;
- (10) Any other factors that are inappropriate for vaccination by investigator's judgment.

8.4 Criteria for withdrawal and termination

- (1) The participant's guardian request to withdraw from the clinical trial;
- (2) Occurrence of intolerable adverse events, whether it is related to the experimental drug or not;
- (3) The health condition of the participant does not permit participation in this study;
- (4) Upon any abnormal clinical manifestations, the participants will be determined by the investigator whether they are related to the vaccine and whether the participants will discontinue the clinical trial early;
- (5) Any other causes judged by the investigators.

If the participant who discontinues the clinical trial early has received the test vaccine, the clinical trial data of the participant will be used for safety analysis. The participants cannot be replaced

during the study. After withdrawal or discontinuation of a trial in a participant who has received the clinical test vaccine, the investigator shall provide the necessary guidance to the participant in any clinical conditions that may arise in connection with the trial and continue the follow-up until the definitive diagnosis established/stable condition/recovery.

9. Study procedure

9.1 Schedule of activities

Table 10 Schedule of activities

Visit Number	0	1	2	3	4	5	6
Visit date	D-14-0	D0	D7 ^d	D28 ^d	D35 ^d	D56 ^d	D208 ^d
Preliminary notice, participant enrollment	X						
Informed consent		X					
Demography		X					
Medical history collection		X					
Physical examination		X					
Screening by the inclusion/exclusion criteria ^a		X		X			
Blood collection		X					X
Vaccination ^b		X		X			
The participants or their guardians/caregiver record safety observations on the diary card/contact card ^c		X	X	X	X	X	
Monitoring of adverse reactions/events (including grade 3 and above adverse events, SAE, AESI) ^c		X	X	X	X	X	X
Record of the concomitant medication/the vaccine usage ^c		X	X	X	X	X	X

- a) Screening by inclusion/exclusion criteria should be performed before each dose of vaccination.
- b) The participants will be observed for 30 minutes to confirm occurrence of adverse event, especially that of acute anaphylaxis; and they will be followed up as required.
- c) Safety observation includes evaluation of the adverse reactions/events and body temperature measurements, the latter of which should be taken daily from day 0 to 7 after the vaccination or when the fever is suspected. The participants record the safety observations on their diary cards within 28 days of each dose of vaccination, and the investigators shall interview the participant regularly to verify and document the adverse events and concomitant medication/the vaccine usage.
- d) Please refer to the “Visit plan” for the time window.

Visit plan:

Visit 0 -day -14~0 - Preliminary notice, participant enrollment;

Visit 1 -day 0 - Enrollment of the eligible participants, blood collection and vaccination of the first dose;

Visit 2 -day 7 (+3 days) after the first dose - verify the safety observation, medication and other vaccination records;

Visit 3 -day 28 (+15 days) after the first dose - verify the safety observation, medication, other vaccination records and vaccination of the second dose;

Visit 4 -day 7 (+3 days) after the second dose - verify the safety observation, medication and other vaccination records;

Visit 5 -day 28 (+15 days) after the second dose - verify the safety observation, medication, other vaccination records and blood collection;

Visit 6 -day 180 (+30 days) after the second dose - verification of SAE and AESI observations, records of concomitant medication use, and other special circumstances through telephone follow-up.

During the clinical trial, if an SAE or AESI occurs, the participant's guardian shall be contacted to assist in providing the corresponding medical records, and efforts shall be made to complete the information collection. If it is indeed impossible to collect the information, "unknown" shall be noted in the relevant information section of the original records.

9.2 Enrollment and informed consent

Distribute the recruitment notice to the guardians of potential participants. Explain the informed consent to the participant in detail. On the basis of voluntary participation, the informed consent will be signed by the participant's guardian and the investigation physician in duplicate; and the participant holds the duplicate. Participants will be recruited in accordance with "8.4 Study Plan".

9.3 Screening and randomization

Volunteers recruited will undergo physical examination with no abnormalities and be screened against inclusion/exclusion criteria. The screening number will be formatted as "S + on-site code + screening sequence number", for example, "SZ0001". Eligible participants after screening will be enrolled and assigned a unique study number in the order of enrollment. Once a study number is assigned, it shall not be reassigned to any other subject. For researchers' numbers of participants, see "7.5.1 Randomization".

9.4 Vaccination

The information of participant and trial vaccine should be checked before the vaccination, and only those who meet the inclusion and exclusion criteria of this clinical trial protocol can be vaccinated. Please refer to "5.5 Route and Schedule of Vaccine Administration" for Immunization Schedule.

9.5 Safety follow-up observation

Observe the participants on-site for adverse events within 30 minutes after each dose of vaccination; and give the participants the diary cards after each dose to record the solicited adverse events (systemic and local) from day 0 to 7 after the vaccination and unsolicited adverse events from day 0 to 28 after the vaccination. Investigators will explain the judgment of adverse events, measurement methods, recording methods, precautions, reporting methods, etc., and distribute diary cards, rulers,

and thermometers. They will also train the participant's guardian on using the thermometer, observing adverse events, filling in the diary card, and make an appointment for the return time. Request the subject's guardian to fill out the diary card in detail from day 0 to 28 after the vaccination to record any clinical symptoms, medications and the use of other vaccines.

Conduct systematic observation 0-7 days after each dose of vaccination. The participant's guardian observes the subject's symptoms and signs every day and fill them in the diary cards for the investigators to collect safety observation data from day 0 to 7. From day 8 to 28, record the adverse events by using the method of voluntary reporting from subject's guardian and regular follow-up by investigators; and at day 28, take back the diary cards. Monitoring of SAEs and AESIs will continue until 6 months after the second of vaccination. SAEs and AESIs from day 29 after the second of vaccination to 6 months after the second will be collected through a combination of telephone follow-up once every 2 months and active reporting by the subject.

The participants should be informed of recording any adverse events at any time. In case of acute allergic reaction, Grade 3 or above adverse event or SAE, they should report to the investigators at any time and the investigators should conduct investigation, verification, and follow-up after learning until the event is resolved so as to finally complete the detailed investigation and follow-up records, which should include following:

- Description of adverse events
- Start time and end time of adverse events
- Severity classification of adverse events
- Correlation with the vaccination
- Laboratory results
- Treatment

If an acute allergic reaction occurs after vaccination, emergency treatment should be provided in time to relieve the pain of the participants as soon as possible. In case of grade 3 or above adverse event or SAE after vaccination, medical advice should be given in a timely manner; if necessary, the relevant on-site responsible personnel may be contacted to activate the green channel for medical treatment. The medication and medical treatments during each follow-up visit should be recorded in detail. If an AESI occurs (see 9.7.1), the investigators should make a judgment based on clinical symptoms and signs. When necessary, clinical samples (such as blood, urine, etc.) should be collected for laboratory tests, relevant questionnaires should be filled out, and follow-up should be conducted until the AESI is resolved.

9.6 Blood sample collection

All participants will have approximately 2-3 ml of venous blood collected before immunization and 28 days after the second of vaccination, respectively. The serum will be separated for antibody detection. The sample numbering rule is "Study Number + Collection Sequence Number".

All samples collected on-site shall be promptly sent to the laboratory, and handover with laboratory personnel shall be completed. Laboratory personnel shall promptly separate the serum from blood samples for serum antibody detection and aliquot them into 2 tubes (Tube A of the blood sample set should contain no less than 0.5 ml for serum antibody detection; Tube B is the backup serum). After serum separation, it should be promptly frozen and stored at -20°C or below. Records should be kept for sample handover, separation, and storage. For all submitted samples, a specimen

submission record should be filled out, and temperature control records during the submission process should be retained.

9.7 Safety Evaluation

9.7.1 Index for the safety observation

Solicited local adverse events (at the vaccination site): tenderness/pain, induration, swelling, erythema, rash, pruritus.

Solicited systemic adverse events (including vital signs) (non-vaccination site): fever (axillary temperature), acute allergic reaction, skin and mucosal abnormalities, diarrhea, anorexia, vomiting, nausea, cough, fatigue, irritability, lethargy.

See "9.7.7 Safety Evaluation Criteria" for details.

Adverse events of special interest (AESI): include Guillain-Barré Syndrome (GBS), convulsion, encephalitis, myelitis, neuritis, Bell's palsy, vasculitis, thrombocytopenia.

9.7.2 Definition of adverse event/reaction

Vaccine safety will be evaluated based on the severity of the local adverse events, systemic adverse events and vital signs as well as their relevance to the vaccination.

All adverse medical events occurring during the trial (i.e. from the signing of informed consent) will be collected and recorded.

(1) Adverse event (AE): All adverse medical events that occur in a clinical trial participant after receiving an experimental vaccine may be manifested as symptoms and signs of illness or abnormal laboratory tests, but unnecessarily have any causal relationship with an experimental vaccine.

(2) Adverse reaction: Any harmful or undesirable reaction to humans that may be associated with an experimental vaccine during a clinical trial. A causal relationship between an experimental vaccine and an adverse event is at least a reasonable possibility in which the relevance cannot be ruled out.

(3) Serious adverse event (SAE): Refers to any of the following events occurring in clinical trial participants after receiving the trial vaccine:

- Result in death.
- Is life-threatening: An event where the participant is at risk of death at the time of the adverse event's onset; it does not refer to an event which hypothetically might have caused death if it were more severe.
- Requires inpatient hospitalization or prolonged of existing hospitalization: (Routine hospital admission such as for antenatal care, labor & delivery is not an SAE)
- Results in a persistent or significant disability or incapacity
- Results in congenital anomalies or birth defects.
- Any other significant medical events (that may not cause death, be life threatening, or require hospitalization) that may, based upon appropriate medical judgment, jeopardize the participant and/or require medical or surgical intervention to prevent one of the outcomes listed above. Examples of such medical events include allergic reaction requiring intensive treatment in an emergency room or clinic, blood dyscrasias, or

convulsions that do not result in inpatient hospitalization.

Events not considered as serious adverse events:

- Routine emergency room visits (including 24-hour observation stays);
- Hospitalization for routine outpatient examinations;
- Hospitalization for social reasons: Such as hospitalization of the subject due to lack of care;
- Hospitalization for surgery scheduled before signing the informed consent form, but if the condition worsens requiring early surgery, it is considered an SAE;
- Routine physical examination hospitalization;

Death itself is an outcome and not regarded as an SAE. The primary cause of death (the main adverse event leading to death) shall be recorded and reported as an SAE. "Death" shall be reported as a consequence of the corresponding adverse event. If there is no definite cause for death to report, death itself may be reported as an SAE.

(4) Suspected and unexpected serious adverse reaction (SUSAR): is a suspected and unexpected serious adverse reaction, for which, the nature and severity of the clinical manifestations exceed the existing information provided in the brochure of the experimental drug investigators, manual of the on-market drugs or summary of product characteristics, etc.

(5) Solicited/unsolicited adverse events: in this study, the solicitation period is from day 0 to 7 after each dose of vaccination, and the unsolicited period is from day 8 to 28. The solicited symptoms occurring during the solicited period are referred to as the solicited adverse events and other symptoms during the solicited period; and all the symptoms during the unsolicited period are referred to as the unsolicited adverse events.

9.7.3 Outcomes of adverse events

Outcomes of adverse events include: (1) recovered, (2) not recovered, (3) recovered with sequelae, (4) recovering, (5) death and (6) lost/unknown.

9.7.4 Correlation of adverse events and vaccines

The investigators should do their best to explain AE and to evaluate its possible causality, that is, the causality between the investigated vaccine and the alternative causes (such as history of underlying disease and the combined treatment), which applies to all AE, both serious and non-serious.

Causality assessments will be determined by the extent to which the events can be reasonably explained in one or more of the following:

A reasonable temporal relationship between the administration of the trial vaccine and the occurrence of adverse events

Reactions of similar nature have previously been observed in this type of vaccine;

Same events have been reported in the literature with regard to the similar types of vaccine;

The occurrence of the event coincided with the vaccination of the administration of the investigational vaccine; and occur again after the re-administration of the vaccine.

The occurrence of the event can be explained by the effects of concomitant medications (vaccines) or the impact of other treatments

AE Causality should be assessed, by the investigator, to ensure whether there is a reasonable possibility that the AE is caused by the administration of the vaccine, based on the following:

General principles for the correlation judgment:

- ✓ **Certainly related:** there is evidence of vaccination with the experimental vaccines; the occurrence of adverse events and the time sequence of the test vaccine administration are reasonable; adverse events are more likely to be explained by the test vaccines than by other causes; positive results after repeated administration of the test vaccine; adverse events are consistent with the prior knowledge of this type or these types of the vaccine.
- ✓ **Probably related:** there is evidence of vaccination with the experimental vaccines; the occurrence of adverse events and the time sequence of the test vaccine administration are reasonable; adverse events are more likely to be explained by the test vaccines than by other causes.
- ✓ **Possibly related:** there is evidence of vaccination with the experimental vaccines; the occurrence of adverse events and the time sequence of the test vaccine administration are reasonable; the occurrence of the adverse events cannot be ruled out as a result of the test vaccine and possibly may be caused by other reasons.
- ✓ **Unlikely related:** there is evidence of vaccination with the experimental vaccines; adverse events are more likely to be caused by other factors; repeated vaccination tests are negative or uncertain.
- ✓ **Not related:** the participants do not use the test vaccine; or the occurrence of adverse events and the time sequence of the test vaccine administration are unreasonable; or there may be other significant factors for the adverse events.

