6.1.2 Derived and Transformed Data

➤ Baseline

The last non-missing assessment on or before the first dose of vaccination will be defined as the baseline.

➤ Date Conversion

Month=days/30.4375, Year=days/365.25, rounding to 1 decimal place.

➤ Adverse Event

Occurrence time of AE (days) = Start date of AE - the corresponding vaccination date

AE duration(days) = End date of AE - Start date of AE + 1

➤ Treatment Emergent Adverse Event (TEAE)

TEAEs are defined as adverse events that occur after the first vaccination (including the day of the first vaccination) or worsen after vaccination. Programming is carried out according to the following rules:

- ❖ If the start date of adverse events is after (including simultaneously) the date of the first vaccination, they will be counted as TEAE.
- ❖ If the start date of adverse events is before the date of the first vaccination, they will be counted as non-TEAE.
- ❖ If the start date of adverse event or the date of the first vaccination is missing, making it impossible to determine whether the adverse event occurred after the first vaccination, then such adverse events shall all be counted as TEAE.

➤ Handling of incorrect vaccination

- ❖ In the immunogenicity evaluation, subjects will be analyzed according to the vaccine they were randomized to receive, in accordance with the Intention-To-Treat (ITT) principle.
- ❖ In the safety evaluation, subjects will be analyzed according to the vaccine they actually received, in accordance with the All Subjects as Treated (ASaT).

➤ Relationship of AEs

- ❖ Related to the study, vaccine means that the relationship between the adverse event and the study vaccine is "possibly related", "probably related", or "definitely related".

- ❖ Unrelated to the study vaccine means that the relationship between the adverse event and the study vaccine is "possibly unrelated" or "definitely unrelated".

➤ **Coding**

AEs, SAEs, and concomitant procedures will be encoded according to version 27.0 of the Medical Dictionary for Regulatory Activities (MedDRA). Concomitant medications/concomitant vaccines will be encoded according to the WHODD_2024-Mar-1 version of the World Health Organization Drug Dictionaries (WHODD).

➤ **Prior and Concomitant Medication**

The determination of prior and concomitant medication uses follows the following rules, respectively:

- ✓ Prior medication, medications with an end date that is before the first vaccination date.

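### The last limb of the 'Not related' category overlaps 'Possibly related', so events that meet the protocol's own definition of an adverse reaction can be left out of the adverse-reaction endpoints

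*Protocol*

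**What the plan says.** Protocol 9.7.4 sets out five causality levels under the heading of general principles. Three matter here.

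- *Possibly related* requires vaccination, reasonable timing, and an event that "cannot be ruled out as a result of the test vaccine and possibly may be caused by other reasons".
- The next level down, *Unlikely related*, requires, among other things, that "adverse events are more likely to be caused by other factors".
- *Not related* is a list of alternatives joined by 'or': the test vaccine was not used, the timing is unreasonable, "or there may be other significant factors for the adverse events".

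Protocol 9.7.2 defines an adverse reaction as an event for which a causal link is "at least a reasonable possibility in which the relevance cannot be ruled out".

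SAP 6.1.2 turns the levels into two classes. The top three count as related. The unrelated class is "possibly unrelated' or 'definitely unrelated", labels that the protocol's scale does not use.

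Protocol 7.2 lists the incidence of adverse reactions at 0-28 and 0-7 days after each dose as the first two safety endpoints. SAP 6.9.2 and 6.9.3 tabulate related SAEs and related AESIs. One of the suspension criteria in Protocol 7.8 is the occurrence of a vaccine-related Grade 4 event.

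**The concern.** A causality scale should give each event one level, and the levels should move in one direction. Here, an event with plausible timing, a vaccine role that cannot be excluded and a possible significant other cause fits two levels at once, and those levels lie on opposite sides of the line between counted and not counted. Nothing tells the investigator which level to choose.

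At stake are the adverse-reaction endpoints and every other output or rule that uses relatedness. The setting gives the overlap room to matter. The solicited systemic events in Protocol 9.7.1 include fever, cough, diarrhea, vomiting and irritability, which in children aged 6-35 months can often have a competing explanation, and unsolicited events are collected up to day 28. In a multi-center trial, sites could also settle the ambiguity differently.

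**Working it through.** The plan gives no figure to reproduce, so the check is a comparison of the texts.

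**1. Is the third ground sufficient alone?** Yes. It is joined by 'or' to the other two. It does not ask for implausible timing, for the other cause to be more likely, or for the vaccine to be excluded.

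**2. Do two levels overlap?** Take a vaccinated child with an event at a reasonable time, where the vaccine cannot be excluded and a concurrent illness, judged significant, may also explain the event.

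| Level (Protocol 9.7.4) | Condition | Met? | Class in SAP 6.1.2 |
|---|---|---|---|
| *Possibly related* | vaccinated; timing reasonable; vaccine not excluded; other reasons possible | yes | related |
| *Unlikely related* | other factors more likely | not established | unrelated |
| *Not related*, third ground | other significant factors may exist | yes | unrelated |

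The event meets the first and third rows. The word 'significant' narrows the third ground but does not remove the overlap, because the other reasons allowed under *Possibly related* include significant ones.

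**3. Is the order consistent?** No. *Unlikely related* needs another cause to be more likely. *Not related*, the more extreme level, needs only that one may exist.

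**4. Does it agree with the endpoint definition?** No. Under 9.7.2 the test event is an adverse reaction, because its link to the vaccine cannot be excluded. Under the third ground it may be recorded as unrelated.

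**5. Does any other rule settle it?** Three candidates were checked.

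- SAP 6.9.1 takes the most related grade when the same AE recurs in one subject. It does not classify a single event.
- Protocol 9.7.6 requires a rapid report if either the investigator or the sponsor cannot exclude the vaccine. This covers expedited reporting and is not stated to govern the endpoints.
- Protocol 9.7.4 asks the investigator to judge whether there is a reasonable possibility of causation. This points towards counting the event, but no precedence over the wording of the levels is stated.

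**6. Can the size be worked out?** Let R be the true proportion of subjects with at least one adverse reaction, and f the share of those subjects whose every reaction is an overlapping event recorded as *Not related*. The reported incidence is then R × (1 − f). The documents give neither R nor f. Note that f is a share of subjects, not of events: a subject with even one other event scored as related stays in the numerator. A share of misclassified events therefore cannot be multiplied directly into a subject incidence.

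One assumption is used throughout: the SAP's two unrelated labels stand for the protocol's two lowest levels. The SAP does not say so. Its term for the top level also differs (definitely related, where the protocol has certainly related).

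**The case against.** The other side has several good points.

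- **The text is narrower than it first looks.** A reader might infer that any conceivable other factor makes an event *Not related*. The wording says 'significant', the levels are only general principles, and both 9.7.2 and the opening instruction of 9.7.4 steer the investigator towards *Possibly related*. This stands: undercounting is a possibility that the text permits, not its expected result.
- **SUSAR reporting.** A reader might infer that expedited reporting is weakened as well. The documents do not support this. Under Protocol 9.7.6 every SAE goes to the sponsor whatever its relatedness, the sponsor makes its own assessment, and either party's doubt triggers a rapid report.
- **Bias between arms.** A reader might infer a distorted comparison. The trial is randomized and double-blind, and Protocol 7.5.2 keeps the vaccination staff, who can see the volume, out of other clinical work involving participant information. Nothing shows that the ambiguity would act differently by arm.
- **Events are not lost.** SAP 6.9.1 reports all AEs and unrelated AEs by group at 30 minutes, 0-7 days and 0-28 days, and lists the unrelated ones. SAP 6.9.2 lists every SAE. The second suspension criterion in Protocol 7.8 (Grade 3 or above in at least 15% of participants) carries no relatedness condition.
- **Limited weight.** Safety is a secondary objective, and no hypothesis in SAP 6.7 uses adverse-reaction incidence.
- **Translation.** The wording may come from translation, which cannot be checked here. It is nevertheless the current text.

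These points limit the reach of the problem. None of them says which level applies to a single event that meets two, and none reconciles the third ground with 9.7.2.

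**Conclusion.** The concern holds as an internal inconsistency. The third ground of *Not related* is sufficient alone, overlaps *Possibly related*, inverts the order with *Unlikely related*, and conflicts with the protocol's definition of an adverse reaction. Because the SAP's related/unrelated line falls within the overlap, events that meet the protocol's own definition can be left out of the 0-7 and 0-28 day adverse-reaction endpoints, the related SAE and AESI tables, and the causality-dependent Grade 4 limb of the suspension criteria.

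The size cannot be estimated from the documents. A reader might want to attach a percentage undercount, but any such figure would rest on assumed shares with no source in the plan. The likely direction, if there is any effect, is towards lower reported absolute rates. The trial's success criteria are not affected. The conclusion rests on the English wording as it stands and on reading the SAP's two unrelated labels as the protocol's two lowest levels.

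**What to change.** 1. In Protocol 9.7.4, reword the third ground of *Not related* so that it applies only when another cause is established and a role of the vaccine can be ruled out. This brings it into line with 9.7.2.
2. State that an event meeting more than one level takes the level closer to related.
3. Reconcile Protocol 9.7.2, Protocol 9.7.4 and SAP 6.1.2 so that the levels are mutually exclusive and carry the same names in both documents. This includes the SAP's possibly/definitely unrelated against the protocol's unlikely/not related. State how *Unlikely related* fits with the 9.7.2 test, since a vaccine role may not be fully excluded there either.
4. If causality calls have already been recorded, present the planned all-AE tables for 0-7 and 0-28 days beside the adverse-reaction endpoints, and disclose the overlap in the report.

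The cost is wording in the protocol, SAP and CRF completion guidelines, plus a training note for sites. The fourth step uses tables that are already planned. The downside is that reported adverse-reaction rates may be somewhat higher.
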